15.4. Confidentiality

General

All information disclosed or provided by Medtronic (or any company / institution acting on his behalf), or collected during the retrospective data collection, including, but not limited to, the clinical investigation plan, the eCRFs and the results/data obtained, is confidential. The investigator or any person under his / her authority agrees to undertake to keep confidential and not do disclose the information to any third party without the prior written approval of Medtronic. Co-Investigators as applicable shall be bound by the same obligations as the investigator. The investigator shall inform the co-investigators of the confidential nature of this project as applicable. Both, the investigator and the co-investigators shall use the information solely for the purpose of the project, to the exclusion of any use for their own or for a third party's account.

Subject privacy

All subject data collected under this CIP will be handled strictly confidential and pseudonymized, no names or initials will be used, but only a numeric code and possibly the data of the year of birth. The same subject identifiers will be used as for the FIRE AND ICE Trial to ensure the correct merge of both data sets for the analyses. All analyses performed will be made on pseudonymized data only. Also all results published based on this retrospective data collection will be without disclosing confidential subject data.

All subject data will be protected against unauthorized access and a decryption takes place only under the conditions by the country-specific law.

15.5. Liability (N/A)

Retrospective data collection only without direct subject involvement.

15.6. CIP Amendments

Approval of amendments to the CIP are required are required at each participating site from the following groups prior to implementation of the revised CIP at the participating site:

- Medtronic
- Principal Investigator (where required by local law)
- Competent / Regulatory Authority (if regulatory approval is required)
- Central IRB / EC

If a CIP amendment occurs, site personnel will need to be re-trained as necessary, and will need to submit any changes to their IRB / ECs as required by the local committee.

In some instances, an amendment may require a change in the data release form. In this case, the investigator must receive an EC / IRB approval / favorable opinion concerning the revised data release form prior to implementation of the change.

15.7. Record Retention

The investigator must maintain confidential all project documentation, and take measures to prevent accidental or premature destruction of these documents. The investigator must retain the related documents at least five year after the completion or discontinuation of this retrospective data collection or longer if required by national legislation. This includes, but is not limited to the following documents:

- Signed CIP and amendments (as applicable)
- Issued regulatory approvals (communication with regulatory authorities / ECs)
- Clinical Trial Agreement
- Signed Data Release Forms
- Subject Identification Listings
- Site team authorizations including training documentation and qualification documentation
- CRF pages
- Lab- and medical files
- Site Close Out Report
- Relevant project communication, including as applicable audit and inspection documentation
- Project reports / final project report

The investigator must notify Medtronic prior to destroying any essential project documents within the specified period following completion or discontinuation of the project.

Medtronic records and reports will be maintained in a password-protected document management system, and paper documents (where applicable) will be stored in secured file cabinets at genae (CRO) during the course the project. Document transfer from genae to Medtronic is part of the defined CRO project closing activities.

After closure of the project Medtronic will archive records and reports indefinitely.

Medtronic Confidential

15.8. Publication and Use of Information

Publications from the FIRE AND ICE Re-Ablations retrospective data collection will be handled according to Medtronic Global Standard Operating Procedures and as indicated in the Clinical Trial Agreement (CTA).

The publication rules are regulated separately and described in detail in a publication plan that is confirmed by the publication committee. The overall process and content of the publication plan is comparable with the FIRE AND ICE Trial. Registering and posting the project results on ClinicalTrials.gov will be done based on the posting rules stipulated.

Medtronic will be responsible for preparing any reports based on the additional retrospective data collection. A final report, describing the results of all objectives and analysis, will be distributed to all investigators, IRBs/ECs and CAs of participating countries when required by local law.

An individual site's study data will be made accessible to the corresponding investigator after the completion of the project, if requested.

All information and documents provided by Medtronic or its representatives are and remain the sole property of Medtronic. The investigator shall not mention any information for any other intellectual property rights.

All results, data and documents, which arise directly or indirectly from this project in any form, shall be the immediate and exclusive property of Medtronic.

Publication Committee

Medtronic will form the FIRE AND ICE Re-Ablations Publication Committee (refer to **Appendix V**). Medtronic personnel may serve as members of the committee. This committee will manage publications with the goal of publishing findings from the data. The publication committee will develop the publication plan as a separate document.

The publication committee's role is to 1) manage and develop elements addressed in the publication plan, 2) execute the publication plan, 3) oversee the publication of primary, secondary and ancillary study results as applicable, 4) review and prioritize publication proposals, 5) provide input on publication content, and 6) determine authorship. In addition, the committee will apply and reinforce the authorship guidelines set forth in the publication plan.

Membership in the publication committee does not guarantee authorship. The committee will meet as needed.

15.9. Suspension or Early Termination

Early termination is the closure of a clinical study/project that occurs prior to meeting defined endpoints or objectives. This is possible for the whole study/project or a single participating site. Suspension is a temporary postponement of study/project activities related to enrollment. This is possible for the whole study/project or a single participating site. If suspension is lifted, the investigator shall assess whether or not to continue the clinical study/project at their site.

Possible reasons for considering suspension or termination of this retrospective data collection include but are not limited to:

- Decision by Medtronic or competent authority

Possible reasons for investigator or participating site termination or suspension include but are not limited to:

- Persistent non-compliance to the CIP (e.g. lack of data entry)
- Noncompliance to regulations and the terms of the CTA (e.g. failure to submit data in a timely manner, failure to follow-up on data queries and monitoring findings in a timely manner, etc.)
- IRB/EC suspension of the participating site
- Fraud or fraudulent misconduct is discovered (as defined by local law and regulations)
- Investigator request (e.g. no longer able to support the retrospective data collection)

Procedures Medtronic-initiated / Regulatory-initiated termination or suspension

- Medtronic will promptly inform the investigators of the termination or suspension and the reasons and inform the regulatory authority(ies) where required
- The investigator will promptly inform the IRB/EC of project termination or suspension
- In the case of project termination, the investigator must inform the subjects; information of the personal physician of the subjects to ensure appropriate care and follow-up is not required, as this is a retrospective data collection only
- In the case of a study suspension, entry of new subject data must stop until the suspension is lifted by Medtronic
- No new assessments or follow-up are part of this retrospective data collection; therefore, no direct impact on the patient care and welfare

Procedures Investigator-initiated termination or suspension

- The investigator will inform Medtronic and provide a detailed written explanation of the termination or suspension.
- The investigator will promptly inform the institution (where required per regulatory requirements)
- The investigator will promptly inform the IRB/EC

Appendix I – List of Participating Countries

Appendix II – List of Participating Sites and Investigators

Appendix III – Data Release Form (DRF)

Appendix IV – Members of Endpoint Review Committee (ERC)

Appendix V – Members of Publication Committee

6. Version History

Version	Summary of Changes	Author(s)/Title
1.0	
• Not Applicable, New Document	[name], Pr. Clinical Research Specialist [name], Sr. Pr. Statistician

Appendix I – List of Participating Countries

(sorted in alphabetical order)

Country

Czech Republic

France

Germany

Hungary

Netherlands

Spain

Switzerland

## 1. Version History

Version	Summary of Changes	Author(s)/Title
1.0	Not Applicable, New Document	[name], Project Statistician

## 2. List of Abbreviations and Definitions of Terms

Abbreviation	Definition
AF	Atrial Fibrillation
AVNRT	Atrioventricular Node Reentrant Tachycardia
Blanking period	The 90-day period after the index ablation
CFAE	Complex fractionated atrial electrogram
CIP	Clinical investigation Protocol
CTA	Clinical Trial Agreement
CTI	Cavotricuspid Isthmus
DMP	Data Management Plan
DRF	Data Release Form
EA	Electroanatomical
ERC	Endpoint Review Committee
LA	Left Atrium
MCAR	Missing Completely At Random
PV	Pulmonary Vein
PVI	Pulmonary Vein Isolation
RA	Right Atrium
RF	Radio Frequency
SAP	Statistical Analysis Plan
SD	Standard Deviation

## 3. Introduction

The purpose of the Statistical Analysis Plan (SAP) for the Fire and Ice Re-Ablations retrospective data collection is to provide pre-analysis documentation and rationale for the statistical procedures that will be employed in the planned analyses that are performed throughout this study. Specifically, this plan outlines methods used in the study's final report, as well as in any planned publications. It does not limit the analysis that will be completed, as further analysis beyond what is specified in this document is likely.

This SAP was developed based on version 1 of the Fire and Ice Re-Ablations Clinical Investigation Protocol (referred to as the CIP in this SAP), dated 20-SEP-2017. It, along with the study's Data Management Plan (DMP) defines the procedures for data review, database cleaning and issuing and resolving data queries as well as the procedures for verification, validation and securing of electronic clinical data systems.

The purpose of the retrospective data collection done for the Fire and Ice Re-Ablations is to gain insight into re-occurrence of atrial arrhythmias resulting in a re-ablation after a performed index ablation procedure. Data to be collected from subject charts includes pulmonary vein anatomy, documented atrial arrhythmias prior to re-ablation, pulmonary vein reconnection, pulmonary vein ablation lesion gaps and gap location, ablation lesions performed during the re-ablation, procedure parameters of the Radio Frequency (RF) or cryo ablation catheter utilized during the re-ablation, and success of re-ablations performed. The resulting data may provide insight into the possible causes for re-occurrence of atrial arrhythmias requiring re-ablation.

## 4. Study Objectives

---

### **Objective: Atrial arrhythmias prior to re-ablation**

Summarize the documented atrial arrhythmias prior to re-ablation

**Endpoint:** Each documented atrial arrhythmia will be classified into one of the following categories:

- Atrial Fibrillation (AF)
  - Paroxysmal
  - Persistent
- Atrial Tachycardia
- Atrial Flutter
  - Typical
  - Atypical

### **Objective: Reconnected pulmonary veins**

Summarize the number of reconnected pulmonary veins

**Endpoint:** Each pulmonary vein will be classified as electrically isolated or not prior to re-ablation.

Electrically isolated is defined as bi-directional block, entrance and exit block of PV potentials.

### **Objective: Number and location of gaps in pulmonary vein ablation lesions**

Summarize the number of gaps and location of gaps present in pulmonary vein ablation lesions

[figure not shown]
**Endpoint:** For a redo conducted with a focal catheter and 3D EA mapping, a gap within the pulmonary vein ablation lesion is defined as an electrically reconnected pulmonary vein which after a single spot reablation the response to re-ablation is either PV re-isolation or PV activation-sequence change. Ongoing PV conduction after a single spot re-ablation is attributed to an additional gap. Additional gaps are defined similarly.

For a redo conducted with no 3D EA Mapping, gap location may have been estimated utilizing a mapping catheter.

Each gap location will be identified by the classifications provided in **Figure 1.**

---

**Figure 1.**

To define the location of a gap, including the differentiation for spot gap or linear gap the ipsilateral LA-PV junction is divided into 6 equally distributed segments; superior, antero-superior, antero-inferior, inferior, postero-inferior, and postero-superior.

Spot gap is defined as millimeter size, requiring only a single application without moving the catheter. Linear gap (larger continuous gap) is defined by requiring multiple applications or drawing of the catheter.

## Objective: Ablation lesion sets performed

Summarize ablation lesion sets created during re-ablation procedure.

**Endpoint:** Each lesion set during re-ablation will be classified into one of the following categories:

- Pulmonary vein isolation (PVI)
- LA AF Trigger
- RA AF Trigger
- Superior vena cava trigger
- Inferior vena cava trigger
- Cavoatrial Isthmus (CTI)
- Mitral valve isthmus or line
- Left sided roofline
- Complex fractionated atrial electrogram (CFAE)
- Posterior wall
- AVNRT ablation
- other

## Objective: Acute procedural success

Summarize acute procedural success as assessed by the sites

**Endpoint:** Definition of success for each lesion set found below

- Pulmonary vein isolation (PVI)
  - Acute failure is defined as inability to isolate the pulmonary vein (minimally assessed for entrance block and, where assessable, exit block). Acute success is defined as the absence of acute failure.
- LA AF Trigger
  - Acute success is defined as elimination of trigger by ablation procedure.
- RA AF Trigger
  - Acute success is defined as elimination of trigger by ablation procedure.
- Superior vena cava trigger
  - Acute success is defined as elimination of trigger by ablation procedure.
- Inferior vena cava trigger
  - Acute success is defined as elimination of trigger by ablation procedure.
- Cavotricuspid Isthmus (CTI)
  - Acute success is defined as bidirectional conduction block at the CTI line
- Mitral valve isthmus ablation
  - Acute success is defined as bidirectional conduction block at the mitral isthmus line
- Left atrial roofline
  - Acute success is defined as confirmed block at the roof line
- Left atrial posterior wall
  - Acute success is defined as confirmed block at the posterior wall
- Complex fractionated atrial electrogram (CFAE)
  - Acute success is defined when ablation of electrograms resulted in termination of atrial fibrillation to sinus rhythm or until all complex fractionated regions were completely eliminated
- AVNRT ablation
  - Acute success is defined as 1) no AVNRT inducibility; 2) no jump; 3) single echo only.
- Other

## Objective: Re-ablation procedure times

Summarize re-ablation procedure times.

### Endpoint:

1. *Total procedure time* is defined as time from first venous access to time of last sheath removal.
2. *Left atrial dwell time* is defined as time from transseptal puncture to time of removal of last sheath from the left atrium.
3. *Fluoroscopy time* is defined as total fluoroscopy time used during the procedure.

## Objective: Re-ablation hospitalization length of stay

Summarize the length of stay during the hospitalization for re-ablation

**Endpoint:** Length of stay is defined as the number of days from admission to discharge.

## Objective: Anti-arrhythmic drug use at re-ablation hospitalization discharge

Summarize the anti-arrhythmic drug use at time of discharge from the re-ablation procedure.

**Endpoint:** Anti-arrhythmic drug is defined as a Class I or III antiarrhythmic drug

## Objective: Summarize adenosine testing

Summarize adenosine testing

**Endpoint:** Adenosine testing utilized at the time of re-ablation.

## 5. Investigation Plan

The Fire and Ice Re-Ablations study is a retrospective chart review on a subset of (at a maximum) 110 subjects from the original FIRE AND ICE randomized trial who had repeat ablation procedures during the trial. The inclusion criteria for the Fire and Ice Re-Ablations study are (1) consent for data collection as required per local law (data release form - DRF) and (2) meeting all entry criteria for the original trial at their time of enrollment in it (e.g., consent to be randomized to cryoballoon ablation or RF ablation for drug-refractory paroxysmal atrial fibrillation, able to comply with study procedure, 18 – 75 years in age, no recent cardiovascular operations, etc.).

One final analysis will be completed. At the completion of the review by the endpoint review committee (ERC), the ERC classifications will be entered into the e-capture.net database (hosted by the contract research organization genae), and the database will be frozen. Analyses comparing randomization arms will not be conducted until after the database is frozen.

The Fire and Ice Re-Ablations study design is a retrospective cohort study. It is noted that while subjects were initially randomized to receive either cryoballoon or RF catheter ablation in the original Fire and Ice trial, non-random consequences of the therapies themselves, as well as potentially non-random decisions affecting subject eligibility (e.g., whether a repeat ablation would be performed) limit the strength of inferences between groups compared to the original randomized trial.

## 6. Statistical Methods

### 6.1. Study Subjects

#### 6.1.1. Disposition of Subjects

Subjects are eligible for the Fire and Ice Re-Ablations study if they were enrolled in the original Fire and Ice trial and followed until a repeat ablation procedure was performed. The 110 subjects meeting these criteria are known at the time of this writing. In the final report, a diagram or figure will describe (at a minimum) the following:

- Number of eligible subjects who agreed to the additional data collection
- Subjects found to be ineligible for any reason that was discovered upon chart review
- Subjects who were eligible and signed DRF, but for whom no endpoint data could be obtained

These will be described by therapy arm wherever appropriate.

## 6.1.2. Clinical Investigation Plan (CIP) Deviations

This study is retrospective, and deviations are expected to be uncommon. Any deviations from the CIP or Clinical Trial Agreement (CTA) observed over the course of the retrospective data collection will be displayed in a listing appended to the final report.

## 6.1.3. Analysis Sets

The full analysis set consists of all subjects who agreed to the additional data collection. The full analysis set will be used for all study objectives.

# 6.2. General Methodology

## 6.2.1. Objective #1: Atrial arrhythmias prior to re-ablation

Summarize the documented atrial arrhythmias prior to re-ablation

### Endpoint Definition

Each documented atrial arrhythmia will be classified into one of the following categories:

- Atrial Fibrillation
  - Paroxysmal
  - Persistent
- Atrial Tachycardia
- Atrial Flutter
  - Typical
  - Atypical
- Other

### Analysis methods

The first re-ablation for each subject will be used for analysis. Each first re-ablation will be grouped into the following categories:

1. atrial fibrillation (paroxysmal)
2. atrial fibrillation (persistent)
3. atrial flutter or atrial tachycardia
4. other

The percent of subjects by indication for re-ablation will be summarized in a frequency table. The distribution of type of arrhythmia will be compared between randomization arms using exact methods.

## 6.2.2. Objective #2: Reconnected pulmonary veins

Summarize the number of reconnected pulmonary veins

### Endpoint Definition

Each pulmonary vein will be classified as electrically isolated or not prior to re-ablation. Electrically isolated is defined as bi-directional block, entrance and exit block of PV potentials.

## Analysis Methods

The first re-ablation for each subject will be used for analysis. The number of electrically isolated pulmonary veins will be assessed for each subject and the number of PVs isolated will be compared between randomization arms using a two-sample t-test. It is anticipated that the majority of subjects will have four major pulmonary veins; LIPV, LSPV, RIPV, and RSPV. If a subject has an anatomy in which electrical isolation of more or less than the four major PVs are tested, the number of electrically isolated pulmonary veins for that subject will be normalized to 4.

In addition, a logistic regression model will be fit, to test whether cryo vs RF therapy affect the odds of pulmonary vein reconnection. In the example code below, observations are successes and trials at the subject level, and SAS proc logistic (using trials events syntax) is used. This model assumes similar probabilities of reconnection for all veins within a subject (e.g., reconnection probability is not significantly different between LSPV, LIPV, RSPV, RIPV). This assumption will be tested using frequency tables and Fisher's exact test to assess whether reconnection rates are independent of treatment group by each anatomic location of ablation. This testing will only be performed for locations with 5 or more subjects treated per arm. Odds ratios and corresponding confidence intervals will be back-transformed into probabilities for presentation purposes.

```
proc logistic;
class rand (param = ref ref = 'RF') <other covariates>;
model N_reconnected/N_possible = rand <other covariates>;
run;
```

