4.1. Background

The FIRE AND ICE Trial was a controlled, prospective, non-inferiority, parallel-group, randomized, interventional, open, blinded outcome assessment (PROBE-Design), multi-centre trial, comparing efficacy and safety of isolation of the pulmonary veins with a Cryoballoon catheter versus a Radiofrequency ablation with a ThermoCool® catheter in subjects with paroxysmal atrial fibrillation¹.

A total of 762 subjects underwent randomization within the FIRE AND ICE Trial: 378 assigned to cryoballoon ablation and 384 assigned to radiofrequency ablation. The mean duration of follow-up was 1.5 years. The primary efficacy endpoint (time to first documented recurrent atrial arrhythmia defined as AF>30s, AT or AFL, AAD prescription or repeat ablation) was reached in 138 subjects in the cryoballoon group and in 143 in the radiofrequency group and the related data published in the New England Journal of Medicine on April 4, 2016². The primary efficacy endpoint was observed to occur at similar rate in the cryoballoon and radiofrequency arms (1-year Kaplan–Meier event rate estimates, 34.6% and 35.9%, respectively; hazard ratio, 0.96; 95% confidence interval [CI], 0.76 to 1.22; P<0.001 for noninferiority). The secondary analyses on reintervention and rehospitalization showed that subjects treated with cryoballoon as opposed to radiofrequency current (RFC) ablation had significantly fewer repeat ablations (11.8% cryoballoon vs. 17.6% RFC; p=0.03), direct-current cardioversions (3.2% cryoballoon vs. 6.4% RFC; p=0.04), all-cause hospitalizations (32.6% cryoballoon vs. 41.5% RFC; p=0.01), and cardiovascular rehospitalizations (23.8% cryoballoon vs. 35.9% RFC; P=0.01) during follow-up. Additionally, both subject groups (Cryo and RF arm) improved in quality-of-life scores after AF ablation³.

After the first ablation procedure, in total 119 re-ablations at 15 sites were performed, thereof 49 in the Cryo arm and 70 in the RF arm. The frequency of re-ablation procedures and energy modality of catheter used during the re-ablation was collected during the FIRE AND ICE Trial, but limited data surrounding the re-ablation procedures were collected.

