13.1. General Considerations

A total of 119 repeat ablations were reported in 110 subjects in the FIRE AND ICE Trial. The primary analysis cohort for this CIP will be subjects that provide informed consent for a retrospective data collection (as required). Of the 110 subjects with re-ablations during the FIRE AND ICE Trial, only those that consent for retrospective data collection will be included in analyses (as required by local law / EC).

The Statistical Analysis Plan (SAP) will be created prior to data analysis and include a comprehensive description of the statistical methods to be included in study reports. Any change to the data analysis methods described in the CIP will require an amendment only if it changes a principal feature of the CIP. Any other change to the data analysis methods described in the CIP, and the justification for making the change, will be described in the clinical study report. Medtronic employees or their designated representatives will perform all statistical analyses.

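### SAP 6.2.2 words its logistic model as a test of the effect of cryo vs RF on vein reconnection, but only re-ablated, consenting subjects enter it and no planned analysis addresses that selection

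*SAP*

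**What the plan says.** SAP 6.2.2 compares the number of isolated veins at the first re-ablation between randomised arms by t-test. It then adds that "a logistic regression model will be fit, to test whether cryo vs RF therapy affect the odds of pulmonary vein reconnection". The code is "model N_reconnected/N_possible = rand <other covariates>", with veins assessed at the redo as the denominator and the covariates left as a placeholder.

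The population is fixed by SAP 6.1.1 and 6.1.3: subjects of the parent trial who had a repeat ablation and agreed to the extra data collection. SAP 6.1.3 adds: "The full analysis set will be used for all study objectives". Protocol 13.1 gives the size of the pool: "A total of 119 repeat ablations were reported in 110 subjects in the FIRE AND ICE Trial".

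Protocol 4.1 reports for the parent trial "378 assigned to cryoballoon ablation and 384 assigned to radiofrequency ablation", and that cryoballoon subjects had "significantly fewer repeat ablations (11.8% cryoballoon vs. 17.6% RFC; p=0.03".

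SAP 5 calls the design a retrospective cohort study. It says that non-random consequences of therapy and non-random decisions to re-ablate "limit the strength of inferences between groups compared to the original randomized trial". SAP 7 describes the objectives as mainly descriptive, but singles out the comparison of mean reconnected veins between arms and gives it a power calculation.

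**The concern.** Having a redo is a post-randomisation event. It differs by arm, and reconnection plausibly contributes to it. Among re-ablated subjects the arms are therefore no longer the groups that randomisation made comparable. An odds ratio in that subset mixes any effect of index therapy on reconnection with the different ways in which patients reached a second procedure.

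SAP 5 recognises this in general terms. SAP 6.2.2 nevertheless asks whether therapy affects the odds, with no reference back. The sensitivity analyses in SAP 6.4 deal with missing data inside the redo cohort, not with entry into it, and no covariates are named. SAP 3 says that the plan covers the final report and planned publications. A p-value below 0.05 could thus be reported as a treatment effect on vein reconnection in the plan's own words.

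**Working it through.** **Inputs.** Randomised 378/384, redo rates 11.8%/17.6% with p=0.03, and 49/70 redo procedures (Protocol 4.1); 110 subjects (Protocol 13.1); planning rates of 36.8% (cryo) and 58.1% (RF) per vein (SAP 7); about 90% with consent and data (SAP 6.4). The documents do not give the arm split of the 110 subjects.

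**1. Reproduce the selection figures.** 0.118 × 378 + 0.176 × 384 = 44.6 + 67.6 = 112.2, against 110 stated. I assume 44/66. Fisher's exact test on 44/378 vs 66/384 gives p=0.031, which agrees with the stated 0.03. No whole number over 378 rounds to 11.8% (44 gives 11.6%, 45 gives 11.9%), so the published rates probably use slightly smaller denominators. For example, 44/374 and 66/376 give 11.8% and 17.6%.

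**2. What the planned model would show at the planning rates.** Odds ratio, cryo to RF: (0.368/0.632)/(0.581/0.419) = 0.42. Mean reconnected veins: 4 × 0.368 = 1.47 (the figure in SAP Table 1) and 4 × 0.581 = 2.32, a difference of 0.85.

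**3. How much selection alone leaves open.** Suppose that everyone re-ablated after cryo would also have been re-ablated after RF. Then 11.8/17.6 = 67% of the RF redo group is comparable with the cryo redo group. Keeping the lowest or the highest 67% of a Binomial(4, 0.581) gives RF means of 1.82 or 2.83. Subtracting 1.47 gives differences of 0.35 to 1.36.

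**4. What the randomised denominators can and cannot give.**
- Cannot: reconnection in everyone. Unmapped veins may be all isolated or all reconnected, so the per-vein rate lies between 0.118 × 0.368 = 4.3% and 4.3% + 88.2% = 92.5% for cryo, and between 0.176 × 0.581 = 10.2% and 10.2% + 82.4% = 92.6% for RF.
- Can: first re-ablation with at least one reconnected vein. With four independent veins, the chance of at least one is 1 − 0.632⁴ = 0.840 (cryo) and 1 − 0.419⁴ = 0.969 (RF). Per randomised subject: 44/378 × 0.840 = 9.8% and 66/384 × 0.969 = 16.7%.

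**5. Power of that composite.** Two-sided 5%, normal approximation: difference 0.0687, standard error √(0.0978 × 0.9022/378 + 0.1666 × 0.8334/384) = 0.0244, z = 2.82, power Φ(2.82 − 1.96) ≈ 80%. Using the published redo rates directly gives 9.9% vs 17.1% and about 82%.

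**6. Bounds for the 10% without data (assumed equal by arm).** None reconnected: 0.9 × 9.8% = 8.8% vs 0.9 × 16.7% = 15.0%, power about 76%. All reconnected: 8.8% + 0.1 × 11.6% = 10.0% vs 15.0% + 0.1 × 17.2% = 16.7%.

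**The case against.** The SAP discloses the limitation in section 5 and calls its objectives mainly descriptive. Objective 2 itself is only to summarise, and the causal verb appears once, in the additional model. Re-ablated patients are also the natural population for a project about recurrences that led to re-ablation. All of this stands, and it makes the fault one of wording and of a missing supportive analysis, not a failure of the design. It does not remove the fault, because the sentence defining the test still states an effect of therapy.

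The composite is partly redundant. Its ratio is 9.8/16.7 = 0.59, and the redo-rate ratio alone is (44/378)/(66/384) = 0.68. On the log scale that is 0.39 of 0.53, so about 73% of the contrast is the redo difference already reported. This stands, and it is why the composite should be supportive only.

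Three stronger readings are tempting, and the documents do not support them:
- *The 378/384 denominators would give an unselected comparison of reconnection.* They would not. Subjects without a redo were never mapped, and the ranges in step 4 are almost uninformative.
- *SAP 7 singles out the causal hypothesis.* It singles out the difference in means tested by the t-test, in non-causal terms.
- *The redo-only result points the wrong way.* That needs invented values. With redo means of 2.0 (cryo) and 1.6 (RF), RF looks better among redos, while counts per 100 randomised (44 × 2.0/378 = 23.3 vs 66 × 1.6/384 = 27.5) favour cryo. At the SAP's own planning rates the RF-to-cryo ratio is 1.58 among redos (2.324/1.472) and 2.33 per randomised subject (39.9/17.1 per 100), so the direction is the same.

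**Conclusion.** The point holds in a limited form. SAP 6.2.2 claims more than its population can support, and neither the disclosure in SAP 5 nor the missing-data analyses in SAP 6.4 closes the gap. At the planning rates, selection leaves a range of 0.35 to 1.36 veins around the unadjusted 0.85. All of that range is on the same side of zero, so the size of the difference is in doubt under these assumptions, but not its direction. The range rests on the planning rates, independent veins and one-directional selection. The composite figures (9.8% vs 16.7%, power 76% to 80%) rest on the planning rates, independent veins and a 44/66 split that the documents do not give. The composite is a randomised comparison of reconnection found at re-ablation. It should not be read as an estimate of reconnection in all randomised subjects.

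**What to change.** 1. In SAP 6.2.2, replace the stated aim of the logistic model with: 'describe the association between index arm and PV reconnection among re-ablated subjects'. Cross-refer to SAP 5.
2. Add a supportive comparison over all randomised subjects (378 vs 384), by the age stratum in Protocol 10.5, of 'first re-ablation with at least one reconnected PV'. Give all/none bounds for re-ablated subjects without data, including the two crossed combinations of arms. State which denominators are used, since the published redo rates seem to rest on slightly smaller ones.
3. State beside it that the composite measures reconnection found at re-ablation, partly reflects the open-label decision to re-ablate and the redo difference already reported, and does not estimate reconnection in everyone randomised.

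**Cost.** Rewording and one table, with no new data: Protocol 15.4 keeps the same identifiers so that the two data sets can be merged. The addition does need a second analysis set in SAP 6.1.3 and an entry in SAP 6.8. Protocol 13.1 limits analyses to consenting subjects where local law or the ethics committee requires it. The sponsor should therefore confirm that non-consenting redo subjects may be counted in the bounds from parent-trial data alone.
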